#### **GLOSSARY OF ABBREVATIONS**

AE Adverse Event

BASEC Business Administration System for Ethical Committees

CRF Case Report Form

CTCAE Common Terminology Criteria for Adverse Events

FADP Federal Act on Data Protection (in German: DSG, in French: LPD, in Italian: LPD)

eCRF electronic Case Report Form FOPH Federal Office of Public Health

GCP Good Clinical Practice

HRA Human Research Act (in German: HFG, in French: LRH, in Italian: LRUm)

ICH International Conference on Harmonisation

ClinO Ordinance on Clinical Trials in Human Research (in German: KlinV, in French:

OClin, in Italian: OSRUm)

SAE Serious Adverse Event

#### 1 STUDY SYNOPSIS

Sponsor /	Changes Investigator				
Sponsor-	Sponsor-Investigator				
Investigator					
Study Title	Arts and culture on prescription. The impact of cultural prescription on the health of the elderly population living in the Lugano municipality – A pilot project.				
Short Title /	population living in the Eugano municipality – A pilot project.				
Study ID	Arts and culture on prescription.				
Protocol Version					
and Date	Version 1 (dated 2/06/2025)				
Study	The study will be registered on the International Clinical Trials Registry Platform (ICTRP) and				
Registration	on the FOPH portal SNCTP (Swiss National Clinical Trial Portal) before it starts.				
Study Category and Rationale	This study qualifies as Risk Category A under ClinO, Article 61, which covers clinical trials with minimal risk. According to ClinO, Article 2, minimal risks refer to interventions that do not exceed those of routine medical procedures, such as non-invasive examinations and standard psychological tests. The study involves cultural and artistic activities (e.g., painting, drawing, dance) as part of the LAC program, which are non-invasive and carry minimal risk. Additionally, it includes blood draws, medical examinations, monitoring through a smartwatch, and questionnaires. While the blood draw and medical examination involve low risk (e.g., discomfort at the injection site), they are common practices, and the smartwatch monitoring is non-invasive.				
Background and Rationale	Cultural prescribing, an innovative approach that integrates arts and culture into healthcare, has shown promise in enhancing well-being across various health conditions. However, little is known about its acceptability among elderly individuals, particularly those managing lifestyle-related pathological conditions. This pilot project aims to explore how older adults (≥65 years) living in the Lugano municipality perceive and engage with cultural prescriptions—recommendations to participate in art workshops, cultural activities, and experiential programs—as part of their healthcare.  Sex and gender are important factors in this study. It is crucial to consider both dimensions not only to ensure equitable engagement with the cultural prescriptions but also to tailor				
	interventions that are more inclusive and effective for different groups. To achieve this, we will aim for a balanced sample with a 50:50 gender distribution. Gender will be integrated into the analysis to identify any differences in engagement or outcomes, ensuring that the interventions are appropriately adapted for all participants.  The study's minimal risks are outweighed by the potential benefits of enhanced mental health				
Risk / Benefit Assessment	and well-being, social connection, and improved health outcomes through engagement in artistic and cultural prescriptions.				
Objective(s)	Primary objective: Explore programme feasibility and acceptability by assessing programme uptake, attendance rates, reasons for non-attendance, and barriers to engagement.  Secondary objectives: Test whether there is any indication of an improvement in health orientation; compare health orientation and health outcomes of those participating in the programme versus the control group.				
Endpoint(s)	Primary endpoints: Uptake and feasibility of recruitment and research procedures. Secondary endpoints: Health Orientation, Mental health and well-being, physiological measures, consultations and hospitalizations/emergency department accesses.				
Study Design	Double-arm feasibility study with a control group, incorporating baseline and post-intervention assessments.				
Inclusion- / Exclusion Criteria	The study population will consist of male and female patients identified by general practitioners who meet the following inclusion criteria:  • Aged 65 or older  • Resident in the Lugano municipality  • Having access to a GP  • Diagnosed > six months with one or more of the following pathological conditions:  Obesity (BMI ≥30); Obstructive sleep apnea syndrome; Type 2 Diabetes Mellitus; Chronic Obstructive Pulmonary Disease (COPD) (GOLD 2 or higher); Uncontrolled hypertension; Uncontrolled gouty arthritis; Metabolic dysfunction and alcohol-related liver disease (MetALD). We will exclude:				

	
 
Individuals who are still in employment (as the study focuses on retirees). Those who undertake occasional freelance work or small consultancies (e.g., fewer than 8 hours per week) may still be eligible, provided their professional activities do not interfere with participation in the study.
 
Individuals diagnosed with moderate to severe dementia or cognitive impairment that affects their ability to provide informed consent.
 

Study procedures	The study will consist of the following procedures:  1. Baseline assessment: Conducted after obtaining informed consent, this includes a blood draw, urine test, completion of questionnaires, and the wearing of a monitoring device.  2. Artistic or cultural prescription assignment: About 3-4 weeks after the baseline assessment, participants will be contacted by a link worker who will identify and match them with a suitable art or cultural program.  3. Program participation: Participants will begin attending the assigned cultural or artistic course, which is scheduled to take place once per week for 1-2 hours over a 6-month period.  4. Second assessment (6-month follow-up): Six months after initiating the intervention, participants will undergo a second assessment, which will include a blood draw, urine test, questionnaires, and device wearing. This is also when we will start conducting the first set of qualitative interviews.  5. Third assessment (12-month follow-up): Six months after the second assessment, participants will complete a long-term follow-up assessment, which will again involve a blood draw, urine test, questionnaires, and device wearing. This is when we will start conducting the second set of qualitative interviews.  Participants will be required to attend all assessments at the Family Medicine Service of the Ospedale Italiano in Lugano. Questionnaires will be completed using a tablet. Nurses and physicians holding a GCP certificate will be responsible for conducting blood draws, reviewing medications, and overseeing the proper use of wearable devices.
Study Duration and Schedule	Estimated duration for the main investigational plan: 18 months.  Planned 06/2025 of First-Participant-In Planned 12/2026 of Last-Participant-Out
	[name]. med. [name]
Investigator(s)	Istituto di Medicina di Famiglia

	Università delle Cuimana italiana
	Università della Svizzera italiana
	Ente Ospedaliero Cantonale
	[name]
	[contact]
	Istituto di Medicina di Famiglia
Study Center(s)	Università della Svizzera italiana
	Ente Ospedaliero Cantonale
	[name]
	Participant characteristics will be summarized at baseline, and statistical significance will be
	set at p<0.05, with results interpreted using p-values and 95% confidence intervals.
	Acceptability will be measured through participant retention and session attendance, and
Statistical	reasons for non-completion will be summarized. Feasibility will be evaluated by analyzing
Considerations:	recruitment time, follow-up completion, and missing data. Primary and secondary outcomes
	will be assessed using paired t-tests, linear mixed-effects models, or repeated-measures
	ANOVA to account for individual variability. Gender will be analyzed as part of all statistical
	evaluations. All quantitative analyses will be performed using Stata or R.
	To ensure privacy, each participant will be assigned a unique code. A list linking these codes
	to participants' names will be stored on a password-protected server (Switchdrive), accessible
	only by the research team. All data from questionnaires, medical visits, smartwatch monitoring,
Data privacy	or blood tests will be stored anonymously, with no participant names, but linked to the unique
	code. Blood and urine samples will be labeled with the unique anonymous code assigned to
	each participant. This system guarantees confidentiality and protects the privacy of participants
	while handling both data and any applicable biological material.
	The scientific value of this study lies in its exploration of the impact of cultural prescribing on
	the well-being of older adults, particularly those managing lifestyle-related conditions. This
	approach is innovative in integrating arts and cultural activities into healthcare, an area with
	limited research in elderly populations. By assessing how older adults engage with cultural
	prescriptions, the study could provide valuable insights into improving healthcare interventions
	for this group, potentially informing future practices.
	The methodology is carefully designed to assess the feasibility and acceptability of cultural
	prescribing through a controlled study, with a control group receiving a cultural activity
	alternative (museum, concert, or show) to allow for comparison. By assigning participants to
	two groups and monitoring health outcomes using statistical methods, the study ensures a
	rigorous and scientifically sound approach that will provide preliminary insights into the
Ethical	effectiveness of cultural prescribing.
consideration	Regarding risks and benefits, the study presents minimal risks, primarily associated with the
	blood draw, medical examination, and monitoring through the smartwatch, which are common
	procedures in clinical research. These risks will be mitigated through appropriate medical
	supervision and participant monitoring. The benefits include potential improvements in mental
	and physical well-being, reduced loneliness, and increased social support through
	engagement in cultural activities.
	Older adults are considered a vulnerable population due to the high prevalence of chronic
	conditions, poverty, and social isolation. We are fully committed to ensuring their protection
	throughout the study. We will take all necessary precautions to ensure their safety,
	understanding, and comfort during participation. Furthermore, we will provide appropriate
	resources and referrals to healthcare professionals if any issues arise during the study,
	whether related to physical or mental health concerns.
	This study will be conducted in compliance with the protocol, the current version of the
GCP Statement	Declaration of Helsinki, the ICH-GCP, the HRA as well as other locally relevant legal and
	regulatory requirements.
L	

#### 2 BACKGROUND AND RATIONALE

Social prescribing is a strategy applied in primary care that involves connecting patients to non-clinical services to improve their health and well-being by addressing social determinants of health. It encompasses various interventions, such as arts-on-referral (i.e., non-medical complementary interventions based on arts), exercise programs (e.g., cycling, dancing, swimming), educational opportunities (e.g., formal learning activities), green gyms (i.e., physical activities in natural environments), and cultural activities (e.g., playing music, painting, drawings), which have been studied for their positive impact on mental wellbeing and positive mood, self-esteem and confidence, quality of life, and their reduction in anxiety, depression and negative mood.

However, there is still a paucity of robust evidence on the effectiveness of the different interventions, especially the mechanisms explaining their effects on health. Moreover, most research has focused primarily on arts-related interventions, and the most reported reasons for referral to a social prescription were anxiety, isolation, and depression. Furthermore, there is little evidence concerning evaluating proactive and "formal" social prescribing, in which primary healthcare teams coordinate and build a network with the social or cultural intervention teams. Moreover, research underlined the importance of the facilitator, also called the "link worker", in mediating between healthcare providers and community services, ensuring patient adherence to the social prescription and engagement.

Despite this growing body of evidence, arts and culture, as forms of social prescription, remain underexplored in many countries, including Switzerland. The promising impact of such programs in other regions highlights the potential for similar outcomes in Swiss communities, where the rich cultural heritage and vibrant arts scene provide an ideal setting for this approach. By launching Switzerland's first cultural prescribing pilot project in Lugano, we aim to build on international evidence and create a tailored program to set a precedent for integrating culture into healthcare across the country.

Due to its cultural landscape, the Lugano municipality presents an ideal setting for a project on cultural prescription. It offers a wide array of activities and a robust network of family physicians who are not only well-integrated into the local healthcare system but also open to testing innovative interventions aimed at improving patient well-being. This collaborative medical community will facilitate recruitment and implementation of the intervention.

Lifestyle-related conditions—such as obesity, insulin resistance, hypertension, and chronic obstructive pulmonary disease —pose a substantial public health burden, contributing to increased morbidity, reduced quality of life, and rising healthcare costs. These conditions are often interconnected, elevating the risk of developing cardiovascular diseases, type 2 diabetes, and other chronic illnesses. Despite their largely preventable nature, they remain prevalent due to complex interactions between genetic predisposition, environmental factors, and behavioural patterns. Addressing these conditions requires a multifaceted approach that includes medical interventions, lifestyle modifications, and supportive social and healthcare policies aimed at promoting sustainable health behaviours. While lifestyle changes and pharmacological treatments remain the cornerstone of management, effectively tackling the psychosocial and behavioural factors that contribute to these conditions is crucial for long-term success. Social determinants of health, including mental well-being, social isolation, and access to supportive environments, play a significant role in the progression and management of these conditions.

Physical activity is a reliable lifestyle indicator and can be monitored to evaluate the impact of lifestyle interventions. Heart Rate Variability (HRV) is a general indicator of cardiovascular health. In particular, HRV is a physiological marker of the autonomic nervous system (ANS) function. Improved HRV generally indicates better autonomic flexibility, good relaxation, and better cardiovascular health. It has been proved that improving awareness of HRV after myocardial infarction through biofeedback exercises may favourably impact HRV regulation and, therefore, cardiovascular health. HRV biofeedback may be a valid instrument for raising awareness on CVD risk. Lifestyle significantly impacts sleep quality, which in turn contributes to cardiovascular risk and plays a central role in exacerbating its consequences. Blood pressure

increase, as well as the other pathological lifestyle repercussions, directly contributes to increased cardiovascular risk.

The impact of illness awareness on disease self-management and health behaviour is well-supported by research, particularly in the context of chronic illnesses. Illness awareness - a patient's understanding of their disease, including its causes, symptoms, treatment options, and the necessary lifestyle modifications - plays a key role in promoting more effective selfmanagement and healthier behaviours. A study by Burton and colleagues 19 found that structured drama and visualization exercises, along with shared storytelling, helped participants shift from denial and frustration to acceptance of their illness, fostering a sense of community, reducing loneliness, increasing perceived social support, and enhancing confidence in sharing their experiences, particularly in in-person settings. Numerous studies suggest that greater acceptance of illness positively influences patients' quality of life and enhances their motivation to engage in behaviours that promote their well-being. Recently, the health orientation construct has been developed as a comprehensive framework to capture individuals' attitudes, beliefs, and proactive engagement with their health. This construct integrates multiple dimensions, including health awareness, motivation for self-care, and behavioural tendencies related to disease prevention and management. It provides a broader perspective on how individuals conceptualize and respond to their health conditions, further highlighting the role of illness awareness in shaping self-management behaviours and overall well-being.

Cultural prescribing, an emerging form of social prescription, offers a promising intervention by integrating non-clinical arts activities into primary care. Engaging patients in arts programs and cultural prescription activities has been shown to enhance their mental well-being, build social connections, and potentially improve their self-management of chronic conditions. Despite its growing use internationally, there is limited evidence of the effectiveness of cultural prescribing in managing chronic illnesses like metabolic syndrome, and the mechanisms underlying its health benefits remain to be fully understood.

The present project proposes a mixed-method study to test the feasibility and acceptability of cultural prescription for patients with lifestyle-related pathological conditions. Additionally, it aims to explore whether there is any indication of improvement in health orientation and health outcomes as a result of the intervention.

According to ClinO, Art. 61, this study falls under Risk Category A (minimal risk). The rationale for this categorization stems from the fact that the study involves procedures that are well-established in research (blood draw, urine test, medical examination, smartwatch monitoring, and completing questionnaires), which are common and have minimal risks. These risks are primarily associated with the physical examination and the blood draw, which are generally safe procedures, and the potential for discomfort or mild anxiety. Additionally, the cultural prescribing intervention (art workshops, cultural activities) poses no more than minimal psychological or physical risk, given the nature of the activities involved.

Regarding the relevance of "sex and gender" dimensions, these factors are indeed pertinent to the study. Sex and gender influence health outcomes and can affect how individuals experience and engage with health interventions. Biological differences (e.g., hormone levels, genetics) and social constructs (e.g., gender roles, expectations) may impact participants' responses to cultural prescribing activities, particularly in the context of older adults with lifestyle-related conditions. Therefore, gender dimensions will be taken into account to ensure that interventions are equitable and tailored to the needs of different participants. This will include analyzing any potential differences in engagement with and outcomes from the cultural prescribing intervention based on gender.

#### 3 STUDY OBJECTIVES AND DESIGN

#### 3.1 Hypothesis and primary objective

Primary objective:

1. Explore programme feasibility and acceptability by assessing programme uptake, attendance

rates, reasons for non-attendance, and barriers to engagement.

#### Secondary objectives:

- 2. Test whether there is any indication of an improvement in health orientation.
- 3. Compare health orientation and health outcomes of those participating in the programme versus the control group.

The study hypothesizes that cultural prescribing (artistic and cultural activities as part of healthcare) will be feasible and acceptable to older adults, and that participation in the program will lead to improvements in health orientation and health outcomes compared to a control group.

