#### 3.3 Study design

The study will follow a mixed-method approach. It will be designed as a **double-arm feasibility study with a control group, incorporating baseline and post-intervention assessments.** A total of 100 participants will be recruited and screened by general practitioners (GPs) collaborating with the Institute of Family Medicine at USI to ensure they meet the inclusion criteria. Of these, 80 participants will be assigned to the experimental group and invited to enrol in an artistic or cultural course, selected from a curated selection based on recommendations from a link worker. The remaining 20 participants, matched to the experimental group in terms of gender, age, and medical condition, will serve as the control group and will not participate in these activities, but will be offered a free ticket for a museum, concert o show. Including a small control group in this feasibility study would allow testing of the randomisation procedure and understanding of how the control group would work. All participants will be monitored over time to evaluate the feasibility of the intervention and to assess its potential short-term and long-term effects, particularly in relation to health orientation and other secondary outcomes.

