#### 4.3 Study procedures

The study will consist of the following procedures:

- 1. Baseline assessment: Conducted after obtaining informed consent, this includes a blood draw, urine test, completion of questionnaires, and the wearing of a monitoring device (smartwatch).
- 2. Assignment to the experimental or control group: Participants will be matched based on key factors such as gender, age, and chronic conditions. Using these criteria, participants will be assigned to either the experimental group, where they will engage in an artistic or cultural activity, or the control group, where they will receive a free ticket to visit a museum, show, or concert. This matching ensures balanced comparison between the two groups.
- 3. Artistic or cultural prescription assignment: About 3-4 weeks after the baseline assessment, participants will be contacted by a **link worker** who will identify and match them with a suitable **art or cultural activity**. Participants in the control group will receive the free ticket at home.
- 4. **Programme participation:** Participants will begin attending the assigned **cultural or artistic activity**, which is scheduled to take place over upt to 25 sessions, **once per week for 1-2 hours**, over a 6 month period.
- 5. Second assessment (6-month follow-up): Six months after initiating the intervention, participants will undergo a second assessment (first follow-up), which will include a blood draw, urine test, questionnaires, and device wearing. This is also when we will start conducting the qualitative interviews.
- 6. Third assessment (12-month follow-up): Six months after the second assessment, participants will complete a third assessment (long-term follow-up or second follow-up), which will again involve a blood draw, urine test, questionnaires, and device wearing.
- 7. Debriefing: Debriefing will involve providing participants with a thorough explanation of the study's purpose, procedures, and findings both during a phone call and in written form once their involvement is complete. This will include answering any questions they may have, clarifying the use of their data, and offering additional information on the results or conclusions of the study. Participants will also be reminded of their rights, including their right to withdraw any personal data if desired, and they will be given the opportunity to provide feedback on their experience.

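### Objective 3 words the arm comparison by participation, and the visit clock and replacement rule leave room to compare starters with all controls

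*Protocol*

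**What the plan says.** **The contrast.** Objective 3 in protocol section 3.1 is to "Compare health orientation and health outcomes of those participating in the programme versus the control group"; the synopsis repeats it ("compare health orientation and health outcomes of those participating in the" programme). The hypothesis in the same section is also about taking part: "participation in the program will lead to improvements in health orientation and health outcomes compared to a control group".

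**Assignment.** Section 3.3 says "80 participants will be assigned to the experimental group and invited to enrol in an artistic or cultural course". For the other arm it says "The remaining 20 participants, matched to the experimental group in terms of gender, age, and medical condition, will serve as the control group". Controls have nothing to start: "Participants in the control group will receive the free ticket at home" (section 4.3).

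**Visit timing.** Section 4.3, step 5: "Six months after initiating the intervention, participants will undergo a second assessment (first follow-up"). Step 6: "Six months after the second assessment, participants will complete a third assessment". The synopsis uses the same clock. Appendix 1 instead places the follow-up visits at +6 and +12 months, with the screening and baseline visit at time 0.

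**Replacement.** Section 5.2 provides for new recruits to take the place of people who leave the study before their artistic or cultural activity begins.

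**Passages that point to assigned groups.** Section 3.3 keeps all participants under observation. The synopsis (number of participants) speaks of differences between the experimental and control groups. Section 4.3 describes the matching as serving a balanced comparison of the two groups.

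**The concern.** Being assigned and taking part are different things in this study. Uptake, attendance and reasons for not attending are the primary question, so the protocol itself expects some of the 80 not to take part. An objective that defines the experimental side by participation can be followed literally, with non-starters left out of that side while all 20 controls stay in.

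That would undo the matching on gender, age and condition, on which the balance of the arms rests. Whether someone starts a course is likely to depend on motivation, mood, mobility and illness, which lie close to the outcomes measured (health orientation, depressive symptoms, loneliness, quality of life). The contrast would then describe people who choose to attend, not people to whom the programme is offered, and it would feed into planning of the future RCT.

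The visit clock matters for a practical reason. If a non-starter's assessment is never scheduled, no later analysis decision can recover the data.

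**Working it through.** **1. Who is on each side, passage by passage**

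| Topic | Points to participation | Points to assignment |
|---|---|---|
| Contrast | Objective 3 (3.1, synopsis); hypothesis | Synopsis, number of participants; 4.3 on matching |
| Follow-up date | 4.3 steps 5–6 and synopsis: from start of intervention | Appendix 1: from baseline |
| Who is followed | 5.2: pre-start withdrawals replaced | 3.3: all monitored; 4.3: all assessments required; 4.4: non-attendance not a listed reason for withdrawal |

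**2. The two clocks.** The link worker makes contact about 3–4 weeks after baseline, and section 4.3 gives each person 1 + 6 + 6 = 13 months in the study. On that clock the last assessment falls about 13 months after baseline; in Appendix 1 it falls at 12. The clocks differ by about a month even for people who start on time. For a non-starter or a control, the section 4.3 clock has no clearly defined origin.

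**3. The plan's own figure.** 80 + 20 = 100 adds up. The sample size is justified by precedent; no effect size, SD, power or uptake rate is given, so there is no power calculation to reproduce. The values below for non-starters are assumptions.

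**4. Bias of a starters-only comparison.** Let q be the share of assigned people who never start, and g the expected change in starters minus that in non-starters when the programme has no effect (in SD). If starters have mean change m, the whole assigned arm has (1 − q)m + q(m − g) = m − qg. Matched controls, who face no start hurdle, are expected to share that mean. Starters minus controls is therefore m − (m − qg) = **qg**.

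**5. Precision by assigned group.** SE = √(1/80 + 1/20) = √0.0625 = 0.25 SD. The 95% half-width is 1.96 × 0.25 = 0.49 SD. The difference detectable with 80% power is (1.96 + 0.84) × 0.25 = 0.70 SD.

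**6. Numbers put in** (normal approximation, two-sided 5%, no true effect; sidedness is not stated and is assumed)

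| q | g (SD) | Starters | Bias qg (SD) | Type I error | Type I error if replaced up to 80 starters |
|---|---|---|---|---|---|
| 10% | 0.2 | 72 | 0.02 | 5.1% | 5.1% |
| 20% | 0.5 | 64 | 0.10 | 6.8% | 6.9% |
| 30% | 0.5 | 56 | 0.15 | 8.9% | 9.2% |
| 40% | 0.8 | 48 | 0.32 | 22.5% | 24.9% |

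Comparing all 80 with all 20, bias from this source is 0 and type I error is 5%.

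**7. Uptake denominator.** If 20% do not start and all of them withdraw and are replaced, 80/0.8 = 100 people are assigned to reach 80 starters. Uptake is 80/100 = 80% with the replaced people counted, and 80/80 = 100% without them. The protocol does not say which denominator applies.

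**The case against.** The strongest reply is that objective 3 is loose shorthand for the experimental arm. Section 3.3 follows everyone, section 4.3 requires attendance at all assessments, section 4.4 does not withdraw people for not attending, section 5.1 restricts no analysis to attenders, and Appendix 1 gives every participant a date. Studying reasons for non-attendance also presupposes that non-attenders stay under study. Starting the intervention might even mean the first link-worker contact, since section 3.4 opens with that. And analysis sets are commonly left to the SAP.

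Much of this stands. A reader might infer that the protocol drops non-starters from the experimental arm; no passage says so. A reader might also infer that non-starters have no follow-up date at all; Appendix 1 supplies one, and the literal section 4.3 clock leaves controls undated too. Section 5.2 covers only people who withdraw from the study, not non-starters who remain.

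A reader might further infer that the bias must favour the programme. That does not follow. Section 5.1 plans pre/post comparisons and possibly repeated-measures models, so a stable difference in level largely cancels and only a difference in change counts. Non-starters who begin worse could regress towards the mean and reverse the sign. Section 3.2 notes that interpretation of the health orientation scale varies by dimension, and section 4.3 foresees adjustment for confounders.

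What the reply does not remove is that the contrast, the visit clock and the replacement rule are all stated in the protocol itself, and they disagree with other passages. This is not detail deferred to an SAP.

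**Conclusion.** The point holds as an ambiguous and internally inconsistent comparison, not as a stated exclusion. The objective and hypothesis are worded by participation, other passages imply assignment, the two visit clocks conflict, and the replacement rule as worded works in one arm only. Together they allow a comparison of self-selected starters with controls who face no start filter.

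The size depends on two quantities the protocol does not give. Across assumed values the bias runs from 0.02 SD, which is negligible, to 0.32 SD, which exceeds one standard error. A middle case of 20% non-starters and a 0.5 SD gap gives 0.10 SD and a type I error of 6.8%. It would favour the programme if non-starters have the worse expected change, which is plausible but not certain.

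The weight is moderate. This is a secondary, exploratory aim of a feasibility study, and even the comparison by assigned group is imprecise. It is still worth correcting before recruitment, because assessments that are not scheduled cannot be recovered.

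**What to change.** - **Objective 3 (section 3.1 and synopsis):** compare all participants assigned to the experimental group with all assigned to the control group, whatever their attendance. Align the hypothesis with this.
- **Visit timing:** date the 6- and 12-month assessments in both arms from one common origin, either baseline or assignment, and reconcile section 4.3 and the synopsis with Appendix 1. A planned course start would not serve, because controls have none.
- **Non-starters:** state that assigned people who never start but remain in the study are assessed at both follow-ups.
- **Replacement (section 5.2):** keep pre-start withdrawals in the assigned-group and uptake denominators even if they are replaced.
- **Participants-only comparison:** keep it if wanted, labelled as supplementary.

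The cost is wording in sections 3.1, 4.3, 5.2 and the synopsis (and Appendix 1 if the origin changes), plus possibly a few more follow-up visits, to which participants have already consented. The estimated difference will usually be smaller than in a participants-only comparison.
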